## Abbreviations:

AE – Adverse event

CT – Computed Tomography

CTV – Clinical Target Volume

GCP – Good Clinical Practice

GTV – Gross Tumour Volume

IMRT – Intensity Modulated RadioTherapy

MDT – Multi-Disciplinary Team

MRI – Magnetic Resonance Imaging

NCI – CTCAE-National Cancer Institute Common Terminology Criteria for Adverse Events

NCRI – National Cancer Research Institute

PET – Positron Emission Tomography

RCR – Royal College of Radiologists

SAE – Serious Adverse event

STH – Sheffield Teaching Hospitals

SUSAR – Suspected unexpected serious adverse event

UKIO – The United Kingdom Imaging & Oncology

## **1.3 Project title**

## The use of PET-MRI scans in radiotherapy planning of patients with head and neck cancer: A single centre pilot study

This is a pilot study to assess whether patients with head and neck cancer can tolerate a PET-MRI scan whilst immobilised in a thermoplastic shell that replicates their treatment position during radiotherapy and to assess whether it can improve accuracy in radiotherapy planning.

### **1.4 STH Project Reference number**

STH 21185

### **1.5 Protocol version number and date**

Version 1.1, 04.02.2022

### **1.7 IRAS number: 286722**

### **1.8 Phase of trial**

Not applicable.

### **1.9 STH Directorate affiliation**

Specialised cancer services directorate

## Section 2 – Research question(s)

The primary research question to be answered in this project is “Are patients with locally-advanced head and neck cancer able to tolerate a PET-MRI scan when they are immobilised in a radiotherapy treatment shell?” This will be assessed by measuring the proportion of patients that complete the full scanning protocol and by obtaining participant feedback on their experience of completing the scan.

The secondary question is “Can a PET-MRI scan fused with a planning CT scan improve the accuracy in radiotherapy planning of patients with head and neck cancer? Accuracy will be assessed by:

1. Comparing the radiotherapy target volumes and radiotherapy plans with and without the use of a PET-MRI scan.
2. Comparing inter- and intra-observer variability in treatment contours with and without the use of a PET-MRI scan within and between oncologists and implications of that.

## Section 3 – Abstract

Patients with head and neck cancers are often treated with radiotherapy. The overall aim of treatment is to cure the cancer whilst minimizing its side effects. These cancers are usually close to the surrounding vital organs which are often affected by the radiotherapy. This can cause side effects such as a dry mouth or swallowing difficulties. Improving the accuracy of radiotherapy planning could help reduce side effects and improve quality of life post-treatment.

To design this treatment, patients undergo a “planning CT scan”, a computed tomography scan. This is obtained while the patient’s head and shoulders are held in position by a custom-made thermoplastic shell. The shell is necessary to ensure that the patient is in exactly the same position every time a dose of radiation is given.

The most important step in planning this treatment is accurately identifying the cancer and the surrounding normal tissues. This is to work out exactly which areas need to be treated and which areas need to be avoided. This is done on the planning CT scan. During diagnosis of cancer, patients undergo other imaging including an MRI (Magnetic Resonance Imaging) scan and a PET-CT(Positron Emission Tomography CT) scan . These are the best imaging modalities for head and neck cancer and feed into the process of identifying cancer accurately. It would be better from a radiotherapy planning perspective if these scans are acquired in the same position as the ‘planning CT scan’.

A PET-MRI scan is a combined MRI and PET scan, which is a new technology available in Sheffield. The current project aims to determine whether patients with head and neck cancers can tolerate an additional ‘PET-MRI’ scan with immobilisation similar to that used during the radiotherapy planning process and to assess if this additional scan helps in improving accuracy in radiotherapy planning.

## Section 4 – Aim of the study

This is a pilot study to investigate the use of PET-MRI scanning in patients with locally-advanced head and neck cancer in radiotherapy treatment planning. The specific objectives are:

### **Primary objective:**

To assess the proportion of patients completing the full PET-MRI scans when they are immobilised in a radiotherapy treatment shell. For patients that do not complete the full scanning protocol, we would determine how long they remain within the scanner.

Subjective assessment of tolerability to the scan, will be determined using a patient tolerability questionnaire (Appendix 1).

### **Secondary objective:**

The secondary objective is to obtain pilot data on assessing the impact of the additional PET-MRI scan on the precision of radiotherapy planning. This will be assessed by comparing the radiotherapy target volumes and treatment plans with and without the use of PET-MRI scan. These tests will be conducted retrospectively and thus will not have any impact on patients' flow through to treatment or their standard care.

### **Exploratory objective:**

To assess whether PET-MRI scanning adds benefit to cancer patient's diagnostic investigations.

## Section 5 –Background

### 5.1 Clinical and Scientific Relevance:

Over the last 20 years, curative treatment of cancers of the head and neck has gradually evolved, particularly for cancers that arise in the pharynx/throat. There has been a progressive reduction in the proportion of patients that have surgery, and a concomitant increase in the proportion receiving radical (curative) chemo/radiotherapy (radiotherapy with or without concurrent chemotherapy). This is because function (speech and swallowing) is generally better preserved for chemo/radiotherapy compared to surgery and surgery and chemo/radiotherapy have similar cure rates.

The overall aim of chemo/radiotherapy treatment is to maintain a high chance of curing a patient's cancer, while at the same time minimising side-effects and maximising longer-term function. All locally-advanced head and neck cancers are in close proximity to vital structures ('organs at risk'), and these structures are often affected by radiotherapy. Frequent long-term side-effects include dry mouth, when the salivary glands are in the radiotherapy treatment fields, and difficulty swallowing due to scarring of the muscles of the pharynx/oesophagus. Technological developments, including Intensity Modulated Radiotherapy (IMRT), have improved the precision of radiotherapy treatment planning, leading to significantly reduced long-term side effects. Further research strategies to improve outcomes are based on improving the accuracy of 'target delineation' which is a critical step in radiotherapy planning. This step includes identifying the gross tumour as well as the surrounding normal structures on scans with high accuracy. Interventions that can improve precision in this process could lead to changes in the overall volume of tissue treated and reduce the overall dose of radiation to surrounding normal structures which could translate to reduced side effects.

Radiotherapy involves delivering high energy X-rays to the primary tumour, nodal metastases as well as the draining lymph nodes which may be at risk of microscopic i.e. subclinical disease, with the objective of killing all of the cancer cells. For patients with head and neck cancers, this treatment is generally given as fractions (doses) of radiation five days a week for six to seven weeks. In order to deliver the radiotherapy

to the same site over 30-35 treatment sessions, the patient position must be consistent and accurately reproduced at each treatment session. This is achieved by using a thermoplastic shell that holds the patient's head and shoulders in position and is secured to the treatment table. Patients undergo a computed tomography (CT) scan wearing the thermoplastic shell which enables a virtual simulation of the treatment. Critically, the planning CT scan is obtained in the same position and using similar immobilisation as the radiotherapy treatment itself.

The most important step in radiotherapy planning is 'target delineation', the process of accurately defining the cancer and nearby normal organs on this planning scan. This dictates the volume of tissue that receives radiation. Other diagnostic scans such as magnetic resonance imaging (MRI) and positron emission tomography CT (PET-CT) scans feed into the target delineation process as oncologists use these images as a guide, but ultimately the contouring and treatment planning is done on the CT planning scan.

Once the gross tumour is contoured, oncologists use a margin to create a clinical target volume. This margin is to account for microscopic spread of cancer cells. Using a smaller margin to set the clinical target volume will reduce the radiation to the surrounding normal structures and eventually can translate into reduced side effects. But the gross tumour volume must be identified accurately to avoid the risk of under-dosing the tumour.

## 5.2 Scientific Justification

MRI is the imaging modality of choice for staging of malignant tumours of the head and neck because of its superior soft tissue detail compared to other modalities. Patients with advanced-stage disease (e.g. T4 tumours or N3 nodal disease) should also have a PET-CT to exclude distant metastatic disease and help guide the decision-making process regarding treatment intent, resectability etc. These scans are performed without patients being in the radiotherapy treatment position, which can then cause difficulties in localisation and using this information to aid target delineation. There is evidence that fusion of the planning CT scan with MRI or PET-CT images can improve the accuracy of radiotherapy planning/contouring and this

accuracy is enhanced if the MRI or PET-CT scans are acquired in the radiotherapy treatment position.

Combining the superior anatomical image quality of an MRI scan with the functional images of a PET scan in a single scanner is a recent development in imaging technology that may provide a more accurate delineation of locally-advanced head and neck cancers. PET-MRI is superior to PET-CT for local staging of nasopharyngeal cancer and differentiated thyroid cancer, with several small studies demonstrating the added value of PET-MRI in head and neck squamous cancer. PET-MRI is not currently in routine clinical use, in part because of access, but it has the potential to transform future patient care. A new University of Sheffield PET-MRI scanner has been installed in 2020. Weston Park Cancer Centre has a national reputation of providing high quality clinical care for patients with head and neck cancer and is one of the top recruiters to UK-wide clinical trials (PET-Neck, De-Escalate, ART-DECO, DARS NIMRAD, COMPARE). The service is enhanced by wider multidisciplinary expertise: excellence in diagnostic radiology and state-of-the-art multimodality image co-registration techniques that have been tested and applied in numerous structural and functional MRI and CT studies. Using PET-MRI to aid radiotherapy planning has not been evaluated anywhere in the world. Therefore, the new PET-MRI scanner in Sheffield represents a ‘window of opportunity’ to exploit such technology and would place Sheffield at the forefront of UK research in this area.

The current study will test the feasibility of PET-MRI in the setting of radiotherapy planning. Pilot data to assess and measure the variance in radiotherapy planning will also be obtained, and would be used to design a larger study if the feasibility was confirmed.

### 5.3 Potential benefit to patients

The current project is a feasibility study to confirm that PET-MRI scans with immobilisation in a radiotherapy shell are tolerated by head and neck cancer patients. At this stage, it is of no direct benefit to patients enrolled on the study, but, if successful, will provide important pilot data that could be used to plan a larger study in the future.

We do not anticipate that the PET-MRI scan will add any new diagnostic information as all recruited patients would have had similar imaging (MRI and PET-CT) already at the time of diagnosis. However, this is an additional and advanced imaging technique where the PET-MR images are reported by an appropriately-trained radiologist. If there is any significant change that could have an impact on a patient's cancer treatment, this will be communicated to the patient by their Oncologist.

Gaining qualitative perspectives of the participant's experience of undertaking a PET-MRI scan will allow the project team to gain valuable insight into potential barriers that could influence the implementation of this imaging modality into standard clinical practice. This will help the team to develop supportive services which will help future patients to successfully complete the scan as part of their routine standard care. Subsequently, this could provide a long term benefit to future patients by providing them with access to a technology that can potentially aid in improving the precision of radiotherapy planning. This can, in turn, have a positive impact on overall outcomes from cancer treatment; in terms of curing cancer as well as reducing side effects.

## Section 6 – Plan of Investigation

### 6.1 Methodology

The current study is a feasibility study of whether patients with locally-advanced head and neck cancer can tolerate PET-MRI scanning whilst being immobilised in a radiotherapy shell. The primary objective will be the assessment of the proportion of patients that complete the full scanning protocol (estimated duration 20-30 minutes). For patients that fail to tolerate the full scan, their duration within the scanning environment will be determined as it may be possible to shorten the MRI component of the scan, thus reducing the scan duration. All recruited patients will have had a staging MRI scan, a CT scan of the chest and upper abdomen as well as PET-CT as part of their investigations for cancer diagnosis which means they have successfully completed the standard scanning protocols for MRI or PET, including the standard contrast agents used for these scans.

Patients that participate in the current study will have an extra PET-MRI scan, which will expose them to a small amount (4 – 6 mSv) of extra radiation.

This PET-MRI scan will be obtained while they are wearing the immobilisation shell. Enrolled patients would have had a trial run of wearing the same shell for their planning CT scan required as part of their standard care for radiotherapy planning. Planning CT scan is generally well tolerated and typically lasts 20 minutes which is relatively shorter compared to the time in the shell for a PET-MRI scan.

Potential obstacles to individual patients are their size (the magnet bore is 60cm which is further narrowed down due to the immobilisation equipment required and may influence who can be recruited), their comfort during the scan, as large upper aerodigestive tract tumours affect swallowing and cause coughing, all of which degrade the quality of the images as well as claustrophobia which may be worsened by the thermoplastic shell. A PET-MRI scan with immobilisation has not been tested before. However, researchers are aware that an MRI scan with similar immobilisation is tolerated by head and neck cancer patients and is in routine use in some radiotherapy centres in the UK to aid radiotherapy planning. Likewise, proton beam therapy which involves radiotherapy treatment with protons requires patients to remain in the immobilisation shell for a significantly longer period than the

conventional linac based planning and treatment. This reassures the study team that a PET-MRI scan with immobilisation in patients with head and neck cancer may be feasible despite the longer duration of the scan.

A subjective qualitative assessment of patient tolerability will be obtained using a patient questionnaire. On completion of the PET-MRI, participants will be asked to complete a bespoke questionnaire about their scan. The questionnaire has been developed by members of the project team and lay representatives (Appendix 1). It explores key elements of the scan process (e.g. patient positioning, the use of contrast agents etc.) identified by the literature base as areas which can act as barriers to successful completion by participants. The questionnaire is composed of a mix of binary (yes/no) Likert-scale and open-ended exploratory questions.

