### 6.10.3 Additional radiation exposure from $^{18}\text{F}$ -2-deoxyglucose

The radioactive isotope  $^{18}\text{F}$  decays by positron emission, having a half-life of 110 min. For 'average' patients, this isotope has an effective radiation dose of 19  $\mu\text{Sv}/\text{MBq}^{14}$ , resulting in an exposure of about 4 – 6mSv from the typical 200 - 300 MBq of  $^{18}\text{F}$  that is used in PET oncology imaging.

| FDG dose reference levels                 |           |           |         |              |
|---|-----------|-----------|---------|--------------|
| Minimum ARSAC Dose Reference Level (DRL): | 100MBq    |           |         |              |
| SPC DRL for GE710 Discovery scanner       | Weight    | DRL       | min/bed | Overlap      |
|   | <115Kg    | 3.5MBq/Kg | 2       | 23
(~50%) |
|   | 115-140Kg | 400MBq    | 2.5     |              |
|   | >140Kg    |           | 3       |              |

This is a standard dose for a diagnostic PET scanning and used widely. Patients will be required to follow radiation protection advice after the scan which includes staying away from pregnant women and young children for about 8 hours while the radioactive tracer can still be in their system.

Patients have their contrast-enhanced radiotherapy planning CT scan as part of standard treatment before the PET-MRI scan. A minimum of 24 hours and maximum of 2 weeks will be maintained between the planning CT scan and the PET-MRI scan.

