## 6.13 Instruments

### 6.13.1 PET-MRI scanner :

The new University of Sheffield PET-MRI scanner has been installed as per standard operating procedures.

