### 6.14 Quality control and Assurance

*Induction:* Induction to all members in the delegation log assisting in conducting this research study will be provided at a setup meeting before commencing recruitment into the study.

*Quality assurance of documentation:* The trial will be conducted in accordance with Good Clinical Practice standards.

*Immobilisation equipment and PET-MRI scanner:* The intervention in this study is the extra PET-MRI scan with immobilisation of head, neck and shoulders. PET-MRI scanning is still relatively a new technology in the NHS; national standardised protocols and quality assurance procedures are not currently available. Immobilisation is achieved using a custom made thermoplastic shell and an MRI compatible board to secure the shell to the scanner couch. This equipment is quite similar to the standard immobilisation used in radiotherapy planning for head and neck cancer.

*Co-registration of PET-MRI images with planning CT images:* Study team will use rigid registrations in Varian's™ Image Registration software. A three point match will allow us to report an RMS value for each registration. The match quality will be assessed qualitatively using split window and blended views, and then approved by a clinician before being used for contouring.

*Study QA team:* This team includes co-investigators with expertise in multimodal image acquisition and co-registration of different imaging modalities. The team would facilitate transfer of confidential data between University of Sheffield Academic Radiology and Weston Park Cancer Centre radiotherapy departments. This team will also ensure accuracy of co-registration of PET-MRI scan images with the planning CT images.

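### Does the 4–6 mSv exposure stated in section 6.1 conflict with the weight-based FDG reference levels in section 6.10.3?

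*Combined protocol and SAP*

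**What the plan says.** Section 6.1 (Methodology) gives the exposure in one line: the extra scan is one "which will expose them to a small amount (4 – 6 mSv) of extra radiation". It attaches no condition on weight or activity.

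Section 6.10.3 is the dedicated section. It gives an effective dose of 19 µSv/MBq and limits that coefficient to average patients ("patients, this isotope has an effective radiation dose of 19" µSv/MBq), "resulting in an exposure of about 4 – 6mSv from the typical 200 - 300 MBq" of tracer used in PET oncology imaging. A table of FDG reference levels follows: a 100 MBq minimum, 3.5 MBq/kg below 115 kg, and a fixed level in the next row ("115-140Kg | 400MBq"). The weight rows carry the label "SPC DRL for GE710 Discovery scanner". The first sentence after the table reads "This is a standard dose for a diagnostic PET scanning and used widely".

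The study scanner is described in section 6.13.1 without a model: "The new University of Sheffield PET-MRI scanner has been installed as per standard operating procedures". Section 6.4.2 sets no weight limit; its only size criterion is a 55 cm hoop. Section 10 treats the extra radiation as the study's sole ethical issue. It describes the dose as a standard diagnostic one and gives no figure in mSv.

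**The concern.** Section 6.1 reads as a statement about every participant, while its source in 6.10.3 is hedged three ways: average patients, an approximate range, a typical activity. The table in 6.10.3 scales activity with weight and runs up to 400 MBq, above the 200–300 MBq behind the range. If the table is the study's dosing rule, heavier participants would receive more than 6 mSv and lighter ones less than 4 mSv. The sentence after the table leads into the study's own post-scan advice, so a reader could take the table as that rule.

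The source of the coefficient is also hard to trace. Section 6.10.3 cites reference 14, an imaging recommendation for head and neck cancers. The one radiation-protection source in the list, reference 16, is cited in section 6.10.1 for gadobutrol safety.

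At stake is the risk statement. Participants gain no direct benefit from the scan, and 4–6 mSv is the only dose figure in the available text. If it understated the exposure of some eligible patients, the description of risk would be too favourable for them.

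**Working it through.** **Inputs** (all from section 6.10.3)
- Coefficient: 19 µSv/MBq = 0.019 mSv/MBq, given for average patients.
- Typical activity: 200–300 MBq.
- Table: 3.5 MBq/kg below 115 kg; 400 MBq at 115–140 kg.

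**Step 1: reproduce the stated range.** Dose = activity × 0.019.
- 200 × 0.019 = 3.8 mSv
- 300 × 0.019 = 5.7 mSv

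To the nearest whole mSv this is 4–6. The multiplication is right.

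**Step 2: compare the typical activity with the table, without any coefficient.** Weight = activity ÷ 3.5.
- 200 ÷ 3.5 = 57.1 kg
- 300 ÷ 3.5 = 85.7 kg

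**Step 3: the weights that give 4–6 mSv if the table governs.** Weight = dose ÷ (0.019 × 3.5) = dose ÷ 0.0665.
- Exact bounds: 4 ÷ 0.0665 = 60.2 kg; 6 ÷ 0.0665 = 90.2 kg
- Rounding to whole mSv, as the protocol does when 3.8 becomes about 4: 3.5 ÷ 0.0665 = 52.6 kg; 6.5 ÷ 0.0665 = 97.7 kg

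The exact bounds are stricter than the protocol's own rounding, since its 200 MBq (3.8 mSv) would fail them. About 53–98 kg is the fairer window.

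**Step 4: nominal dose by weight if the table governs and 19 µSv/MBq holds at every weight.**

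| Weight | Activity (MBq) | Dose (mSv) |
|---|---|---|
| 50 kg | 175 | 3.3 |
| 70 kg | 245 | 4.7 |
| 90 kg | 315 | 6.0 |
| 100 kg | 350 | 6.65 |
| 115–140 kg | 400 | 7.6 |

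The last row is 7.6 ÷ 6 = 1.27, or 27% above the stated upper bound.

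**Step 5: dependence on the coefficient.** For 400 MBq to stay within 6 mSv, the coefficient must be at most 6 ÷ 400 = 0.015 mSv/MBq, which is 1 − 15/19 = 21% below the stated value. At 15, 16, 17 and 18 µSv/MBq, 400 MBq gives 6.0, 6.4, 6.8 and 7.2 mSv. The protocol gives no coefficient for heavier patients, so these values only show the range.

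**Step 6: does the table govern the study scan?**
- The table is headed as reference levels, and its weight rows are labelled for one named scanner. No section links that scanner to the study PET-MRI scanner.
- The sentence after the table speaks of one standard dose. It fits the 200–300 MBq paragraph at least as well as a table of several levels.
- Section 6.14 says of PET-MRI that "national standardised protocols and quality assurance procedures are not currently available". That concerns protocols and quality assurance in general and does not settle the administered activity.

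Steps 2 to 5 therefore rest on a premise that the documents do not establish. Without it, Step 1 stands and no understatement is shown.

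**The case for a change.** The strongest case for a change is that a gap remains on either reading. If the table governs, 4–6 mSv does not cover every eligible weight: even with generous rounding, 400 MBq lies outside it. If the table does not govern, no available section states the activity for the study scan, because the 200–300 MBq describes PET oncology imaging in general. Section 10 makes this exposure the study's one ethical issue, and a few lines of text would settle the matter.

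Part of this stands. Section 6.10.3 does not say whether its table applies to the study scan. Section 6.1 drops the qualifiers. The titles of references 14 and 16 suggest that citation numbers were mixed up, although neither source can be consulted here.

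The inference that the plan must change does not stand. Section 6.1 is a summary line, and the qualifiers are in the section devoted to the subject. Section 10 rests on the dose being a standard diagnostic one, with no ceiling in mSv; a table of PET reference levels would not obviously contradict that even if it applied. The largest figure, 7.6 mSv, applies an average-patient coefficient to people of 115–140 kg. How many such patients could be scanned is unknown: section 6.4.2 requires passage through a 55 cm hoop, and section 6.1 notes a 60 cm bore narrowed further by the immobilisation equipment. Neither is a weight limit, so patients between about 90 and 115 kg may well be eligible. Consent pages and appendices are not in the available text, so what participants are told cannot be judged.

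**Conclusion.** The concern does not call for a change to the plan. The 4–6 mSv figure follows from the protocol's own inputs (3.8–5.7 mSv, rounded) and is not an arithmetic error. A departure from it depends on two assumptions that the documents do not make: that the reference-level table sets the activity for the study scan, and that 19 µSv/MBq holds at all weights. Under both, the range would miss patients below about 53–60 kg, where it overstates, and above about 90–98 kg, where it understates, to a nominal maximum of 7.6 mSv in the 115–140 kg row.

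What is left is clerical: a qualifier missing from a summary line, a table whose applicability is not spelled out, and a likely slip in reference numbering. The wording of sections 6.1 and 6.10.3 should be reconciled whenever the text is next revised; no administered activity is suggested here. The primary outcome is the proportion of ten patients completing the scan, and the secondary work compares contours and plans. No dose figure enters either, so design, sample size, analysis and conclusions are the same whichever reading is correct.
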